#### 4.3.1 Regulation success based on the feedback signal (CRED-nf 5a)

A graphical depiction for summary statistics of the raw data for each session in the regulation condition will be provided for the following variables

- percentage success defined to be the number of sample points with online oxygenated haemoglobin values were smaller than the predecessor divided by the total number of sampling points (roughly  $10^5$ ). This is a surrogate for the proportion of time for which the patient experienced “success” though a maximum/minimum picture size could not be exceeded and each step was so small that it could not be perceived.
- minimum picture size (12 per patient) as one measure of success for the feedback
- mean picture size (12 per patient) as a second measure of success for the feedback

Transfer condition

- a graphical representation as with the regulation condition will be provided

Note that after session 6, the selection of pictures was changed to avoid habituation effects.

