Intervention. *fNIRS neurofeedback:* The fNIRS neurofeedback training will be delivered in 12 individual sessions (60 min) over 8 weeks. Personally salient binge food stimuli (and matched neutral stimuli, i.e., household items) will be pre-selected from validated databases. The fNIRS neurofeedback protocol will include a *localization trial* at the outset, during which the individual target area in the prefrontal cortex (e.g., dorsolateral, orbitofrontal) that demonstrates reliable activation differences in response to food stimuli compared to rest, will be selected for training (region of interest, ROI). Detailed working instructions will be derived from pilot measurements. The localization trial will include a rest period, a perceptual food cue exposure (“watch”), a craving food cue exposure (“allow yourself to crave”), and a perceptual neutral cue exposure (household items). The *neurofeedback trials* will include a rest period and regulation food cue exposure (“reduce craving”), followed by rest and reinforcement. During food cue exposure, each food cue

is presented with variable size according to the change in percent blood oxygenation level dependent signal, relative to the preceding fixation block. The goal is to reduce craving by decreasing the size of the food cue. For optimal learning, cognitive-behavioral techniques will be used such as information, reinforcement and self-reinforcement, guided discovery of self-regulation skills, cognitive restructuring, goal setting and planning of transfer into daily life, and homework assignments.

Control. Two control conditions will be used: (1) *EEG neurofeedback*: A validated food cue-based EEG training protocol (high beta training) will be used with 12 individual sessions (60 min) over 8 weeks. This condition serves to examine the comparative efficacy and specificity of changes. (2) *Delayed treatment control condition*: The untreated group will not receive any treatment over 8 weeks, but will afterwards be offered fNIRS neurofeedback. This control condition is essential for examining basic efficacy.

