### **Visual Feedback Signal**

The online feedback was visually displayed on the screen as an individually appetitive food picture via a python built-in function. The size of the picture visualized the neural activity level in the chosen region of interest channels continuously (Item 4b and Item 4c of the CRED-nf checklist). Precisely, the oxygenated hemoglobin value for the region of interest (i.e., the average of the two channels that were selected as region of interest) for a given time point was compared to the oxygenated hemoglobin value for the region of interest at the preceding time point. The goal in the NF task was to increase the oxygenated hemoglobin value. Thus, if the oxygenated hemoglobin value exceeded the previous value, the picture size was reduced by the constant factor 0.01, if the oxygenated hemoglobin value was less than the previous value, the picture size was increased by the constant factor 0.01. Each new picture (of a total of  $n = 12$  pictures) started with a picture size value of 1. The maximum picture size was defined by 1, the minimum picture size by 0.1. For these values, the picture size remained constant if participants decreased (for the maximum picture size) or increased (for the minimum picture size) their oxygenated hemoglobin value further. Nevertheless, these trials still count as success trials.

In the transfer condition, participants did not get real-time feedback. Instead, they were displayed the picture size they had reached by the final 2s of the experiment.

As outcome variable for the feedback condition, the minimum picture size, the mean picture size, and the percentage of successful trials were derived. For the transfer condition, the picture size displayed to the participants was derived as outcome variable.

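### SAP 4.3.1 scores fNIRS percentage success in the opposite direction to the feedback that the SAP appendix describes

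*SAP*

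**What the plan says.** SAP 4.3.1 lists three per-session summaries for the regulation condition, to be shown graphically. The first is "percentage success defined to be the number of sample points with online oxygenated haemoglobin values were smaller than the predecessor", divided by all sampling points (roughly 10^5). The SAP calls it a surrogate for the time during which the patient experienced success. The second is "minimum picture size (12 per patient) as one measure of success for the feedback", and the third is mean picture size.

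The SAP appendix, under Visual Feedback Signal, describes what patients received. "The goal in the NF task was to increase the oxygenated hemoglobin value". The step rule was that "if the oxygenated hemoglobin value exceeded the previous value, the picture size was reduced by the constant factor 0.01", and "if the oxygenated hemoglobin value was less than the previous value, the picture size was increased by the constant factor 0.01". On the limits it says: "The maximum picture size was defined by 1, the minimum picture size by 0.1". Each picture started at size 1. The appendix notes that the size stays constant when the value falls further at the maximum or rises further at the minimum, and then adds: "Nevertheless, these trials still count as success trials".

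Protocol 1.2.1 says which way the picture should move: "The goal is to reduce craving by decreasing the size of the food cue".

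**The concern.** The two SAP passages define success in opposite directions. A fall in oxygenated haemoglobin enlarged the picture, which is the unwanted outcome in the appendix and in protocol 1.2.1, yet 4.3.1 counts that sample as a success. No passage in either document names a fall as the target.

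Percentage success is the first measure listed for CRED-nf item 5a, which asks for regulation success on the feedback signal. Scored literally, sessions with better regulation would plot as worse, and the other two measures in the list would appear to disagree with it. The label would also mean different things in the two neurofeedback arms. SAP 4.4.1 counts an EEG trial as successful when beta activity is below baseline, and protocol 1.1 gives lowering high beta as its example of EEG training.

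**Working it through.** The plan states no figure for this measure, so there is none to reproduce. The check is a comparison of the rules followed by an illustration.

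**Step 1: set the rules side by side.**

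| Oxygenated haemoglobin vs previous sample | Picture (SAP appendix) | Wanted? (protocol 1.2.1) | Scored in SAP 4.3.1 |
|---|---|---|---|
| Rises | Shrinks by 0.01 | Yes | Not success |
| Falls | Grows by 0.01 | No | Success |
| Ties | Not stated | – | Not success |

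**Step 2: derive the relation.** The shares of rises, falls and ties sum to 1. So the 4.3.1 share = 1 − rewarded share − tie share. With no ties, an assumed rewarded share of 0.60 gives 1 − 0.60 = 0.40. An assumed improvement from 50% to 60% would plot as a decline from 50% to 40%.

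**Step 3: illustrate against picture size.** The appendix rule was simulated with step 0.01, limits 0.1 and 1, start at 1, 12 pictures and 10^5 samples. Two things are assumed because the documents give no figures: samples are independent without ties, and the probability p of a rise lies between 0.40 and 0.60.

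| p | Rewarded share | 4.3.1 share | Mean picture size | Falls at maximum size | Rewarded share plus falls at maximum |
|---|---|---|---|---|---|
| 0.40 | 0.401 | 0.599 | 0.979 | 0.197 | 0.599 |
| 0.45 | 0.450 | 0.550 | 0.956 | 0.100 | 0.550 |
| 0.48 | 0.483 | 0.517 | 0.875 | 0.036 | 0.518 |
| 0.50 | 0.498 | 0.502 | 0.639 | 0.010 | 0.509 |
| 0.52 | 0.520 | 0.480 | 0.318 | 0.003 | 0.522 |
| 0.55 | 0.551 | 0.449 | 0.184 | 0.001 | 0.551 |
| 0.60 | 0.601 | 0.399 | 0.142 | 0.000 | 0.601 |

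As regulation improves, the mean picture shrinks from 0.979 to 0.142 while the 4.3.1 share drops from 0.599 to 0.399. A correctly directed measure moves against picture size; this one moves with it.

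**Step 4: examine the limits separately.** The last column shows the corrected direction with falls at maximum size also credited, which is one reading of the appendix sentence. For p below 0.5, and while the lower limit is not reached, falls that move the picture must balance rises in the long run. The share of falls at the ceiling is then about (1 − p) − p = 1 − 2p, which is 0.20 at p = 0.40 and 0.10 at p = 0.45 (simulated 0.197 and 0.100). Under that reading a poor regulator at p = 0.40 scores 59.9% and a good one at p = 0.60 scores 60.1%. The measure could not tell them apart.

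**The case against.** The strongest reply is that little depends on this variable. It appears as a graphical summary, and SAP section 4 calls the neurophysiological analyses explorative. The within- and between-session models (4.3.2) use beta, the regulation-outcome model (4.3.3) uses mean picture size, and the primary analysis (4.1) is separate. A reversed curve would stand beside two picture-size displays that contradict it, so it could well be noticed. All of this stands, and it sets the severity. One qualification is that SAP 4.3 drops the GLM if mean explained variance at baseline is below 15%. The 4.3.1 displays would then carry more of the evidence on fNIRS regulation.

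SAP 4.3 also calls the fNIRS plan temporary. That makes correction timely but does not make the rule right.

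A reader might infer that the trial will report failures as successes. The documents do not show that. The scoring code is not given, and 4.3.1 may contain only a wording slip. The appendix separately names the percentage of successful trials as an outcome, in text where raising the value is the aim.

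A reader might also infer that the limit rule adds error on top of the reversal. It does not: 4.3.1 as written already counts every fall, including those at maximum size. The limits matter only once the direction is corrected. Even then the appendix sentence is ambiguous, because it can be read as covering both limits or only rises at the minimum.

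**Conclusion.** The contradiction in direction is real, lies within the SAP, and is not resolved elsewhere in either document. If 4.3.1 is applied as written, the plotted percentage success is the complement of the rewarded share apart from ties, its session trend reverses, and it conflicts with the two measures next to it.

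The practical size is unknown because no success rate is documented. Without ties the error in level is |1 − 2p|, where p is the rewarded share: 20 percentage points at an assumed 0.60 and 4 points at 0.52. The reversal of trend does not depend on that size. The simulated figures rest on independent samples and an assumed p and serve only as illustration.

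The damage is limited to a descriptive CRED-nf 5a display, so this is a should-fix. It gives no ground for doubting the primary result, the beta models or the regulation-outcome model.

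**What to change.** 1. Check the feedback code to confirm that rising values shrank the picture, and check the scoring code to see which direction it counts.
2. If the feedback code agrees with the appendix, change 4.3.1 to count samples larger than the predecessor, and align the scoring code if needed. If it does not agree, the appendix is the text to correct. Either way the SAP should hold one definition that matches the feedback delivered.
3. Replace the ambiguous limit sentence: a rise at minimum picture size counts as success, and a fall at maximum size does not. State how ties are scored.
4. Before reporting, verify that percentage success correlates negatively with mean picture size.

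The cost is one word in 4.3.1, a sentence or two on limits and ties, at most one sign in the code, and one correlation check. It fits the SAP update that section 4.3 already promises.

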### 4.3 Analysis of fNIRS data

Certain aspects of the analysis of fNIRS data have not yet been clarified so that we now present only a temporary plan to be updated in the next version of the SAP.

The pre-processing of the fNIRS data follows standard procedures and is described below (appendix 6.11). After converting the raw data to haemoglobin concentrations, these are analysed in a general linear model (GLM) where they are treated as the dependent variable with the predicted time course as the independent variable (design matrix). The model estimates a weighting for this predicted time course (referred to here as  $\beta$ ).

The ability of the GLM to model the data may be very limited. In such cases, the type I error is not likely to be inflated, but the type II error can be extremely large, i.e. regardless of the effect size, the model will have very low power. If the mean explained variance of the GLM at baseline is below 15%, then the model will be deemed inadequate and will not be used.

In the standard pre-processing pipeline, outliers are identified on the task and section level and removed. The number of such data (participants) will be reported by session and task (Item 3e of the CRED-nf checklist) and in sensitivity analyses their effect will be studied.

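### SAP 4.3.1 counts falls in oxygenated haemoglobin as fNIRS regulation success, whereas SAP 6.11.3 says that rises were the goal and were rewarded

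*SAP*

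**What the plan says.** SAP 4.3.1 lists three measures of regulation success to be shown graphically per session: percentage success, minimum picture size and mean picture size. Percentage success divides the "number of sample points with online oxygenated haemoglobin values were smaller than the predecessor" by all sampling points. The section calls it a surrogate for the time in which the patient experienced success, and notes that the picture could not go beyond its size limits.

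The Visual Feedback Signal part of SAP 6.11.3 describes the training: "The goal in the NF task was to increase the oxygenated hemoglobin value". Two step rules follow: "if the oxygenated hemoglobin value exceeded the previous value, the picture size was reduced by the constant factor 0.01" and "if the oxygenated hemoglobin value was less than the previous value, the picture size was increased by the constant factor 0.01". Each picture starts at size 1, which is also the maximum; the minimum is 0.1. At a limit, the size does not change for a fall at the maximum or a rise at the minimum. The text then adds: "Nevertheless, these trials still count as success trials". It closes by saying that, for the feedback condition, "the minimum picture size, the mean picture size, and the percentage of successful trials were derived".

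Protocol 1.2.1 fixes what counts as reward in terms of the picture: "The goal is to reduce craving by decreasing the size of the food cue". It does not say which direction of the haemoglobin signal shrinks the picture. SAP 4.3 introduces the fNIRS analyses with the caveat that "we now present only a temporary plan to be updated in the next version of the SAP".

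**The concern.** The two SAP sections give opposite signs to the same event. A fall from one sample to the next is a success in 4.3.1. In 6.11.3 it is a move away from the goal and enlarges the picture. Both cannot describe the same training.

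Percentage success is one of three measures planned for CRED-nf item 5a, the report of whether patients could regulate the signal. Section 4.3.1 is also where SAP 4.3 states which haemoglobin direction is success, so an analyst working from that section would take the sign from it. If rises were rewarded and the measure were coded as 4.3.1 is worded, better regulation would plot as lower success, next to two picture-size measures pointing the other way.

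**Working it through.** The plan gives no figure to reproduce here. The check compares definitions, with a little arithmetic.

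**Inputs.** Success rule: SAP 4.3.1. Goal, step of 0.01, starting size 1 and limits 0.1 and 1: SAP 6.11.3. Smaller picture as the aim: Protocol 1.2.1. I read the constant factor of 0.01 as an additive step.

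**1. Direction, case by case.**

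| Change from previous sample | Picture (6.11.3) | Towards the 6.11.3 goal? | Success under 4.3.1? |
|---|---|---|---|
| Rise | shrinks by 0.01, unless at 0.1 | yes | no |
| Fall | grows by 0.01, unless at 1 | no | yes |
| No change | not stated | no | no |

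For every change that is not a tie, the two sections disagree.

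**2. Relation between the two scores.** Let R, F and T be the numbers of rises, falls and ties, with N = R + F + T.

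- Success as written in 4.3.1 = F/N.
- Share in the rewarded direction under 6.11.3 = R/N.
- Hence F/N = 1 − R/N − T/N. With no ties this is 100% minus the rewarded share.
- The gap is F/N − R/N = 1 − 2R/N when T = 0.

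Illustrative values only, since the documents give no rise share:

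| Rewarded share R/N | 4.3.1 as written | Gap |
|---|---|---|
| 40% | 60% | +20 points |
| 50% | 50% | 0 |
| 52% | 48% | −4 points |
| 60% | 40% | −20 points |

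SAP 6.11.3 describes a signal low-pass filtered at 0.4 Hz, so successive changes are correlated and the actual share may lie close to 50%. The gap in points would then be small, but the ordering of patients is reversed at any spread of shares.

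**3. Against picture size.** Take ten changes from size 0.50, away from both limits, with no ties.

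- Patient A, 6 rises and 4 falls: size 0.50 − 0.06 + 0.04 = 0.48; 4.3.1 scores 4/10 = 40%.
- Patient B, 4 rises and 6 falls: size 0.50 − 0.04 + 0.06 = 0.52; 4.3.1 scores 6/10 = 60%.

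Patient A ends with the smaller picture, the result the protocol wants, and gets the lower success score.

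**4. Which section is likelier to describe delivery.** In 6.11.3 the stated goal and both step rules agree. SAP 6.11.1 selected the trained channels with a Go/NoGo localizer for regions involved in cognitive control, which fits training the signal upwards. Protocol 1.2.1 does not decide the matter, because it names only picture size. So 6.11.3 is likelier, but only the feedback script can settle it.

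**5. The sentence on size limits.** "Nevertheless, these trials still count as success trials" follows a sentence with two cases, a fall at maximum size and a rise at minimum size. If it covers both, a fall at size 1 is a success, contrary to the goal in the same section. If it covers only the second, a rise at 0.1 counts although the picture cannot shrink further, which is consistent with the goal. The text allows both readings. Every picture starts at the maximum, so the first case can arise from the first sample. Section 4.3.1 does not invoke this rule; it counts by sign of change alone.

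**6. Where the measure is used.** Percentage success appears in the 4.3.1 plots. The primary analysis (4.1) uses counts of binge-eating episodes, 4.3.2 uses β values and 4.3.3 uses mean picture size. None takes percentage success as an input.

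**The case against.** The strongest reply is that this is a wording slip with little consequence. The fNIRS section declares itself provisional, the measure is plotted and not tested, and 6.11.3 reports in the past tense that the percentage was derived, so the computed variable may already have the right sign. All of that stands, and it limits the weight of the point. It does not remove the conflict: 4.3.1 does not mark its definition as unsettled, so the wording could pass unnoticed into the update.

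A second reply concerns the size limits. The word *Nevertheless* fits the rise at minimum size well: right direction, no visible gain. A reader might infer that the SAP knowingly credits falls at maximum size, so that good and poor regulators would score alike. The documents do not establish this. The sentence is ambiguous, it speaks of trials while the step rule works per time point, and 4.3.1 does not use it. What stands is a request for clarification.

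A third reply concerns size. Large contrasts between patients need rise shares well away from 50%, and the documents supply none. This is correct, so the percentages above serve only as illustration. The contradiction does not depend on them.

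**Conclusion.** The conflict between SAP 4.3.1 and 6.11.3 is plain on the text and unreconciled; confidence in that is high. Confidence that 6.11.3 is the correct description is moderate. On that assumption, and ignoring ties, percentage success as written is 100% minus the rewarded share and moves against the picture-size measures beside it. Its size in points cannot be stated, because the rise share is not given.

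The consequence is confined to one descriptive CRED-nf 5a measure, so this is a low-priority correction. Three stronger readings go beyond the documents:

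- That patients were trained in the wrong direction. No section says so, and the protocol names no haemoglobin direction.
- That the derived data are reversed. The SAP does not show the code for this variable.
- That efficacy conclusions are at risk. The primary test, the β models and the 4.3.3 model do not use percentage success.

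**What to change.** - Check the script that set the picture size, and the code that derived percentage success.
- If rises were rewarded, change *smaller* to *larger* in the 4.3.1 definition. If falls were rewarded, correct the goal and both step rules in 6.11.3.
- State in 4.3.1 that a smaller picture means better regulation, so that all three measures have a declared direction.
- Reword the size-limit sentence in 6.11.3 so that a sample at 0.1 or 1 counts as success only if the change was in the rewarded direction, and say whether the unit is a sample or a trial.

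These edits belong in the SAP update announced in 4.3. The cost is one script check, a one-word change if rises were rewarded (slightly more if falls were), and two clarifying sentences. No new data are needed and no planned test changes.

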#### 4.3.2 Within-session and between-session comparisons (CRED-nf 5b/5c)

The  $\beta$ -values for the two particular channels of each patients' individual ROIs will be analysed. Since the predicted time course in the first and second half of the regulation block and also between blocks is identical, a comparison of  $\beta$  amounts to a comparison of the optimal weighting of this predicted time course. As noted above, this can be difficult to interpret: e.g. an increase from 0.8 to 1 could indicate that the response followed the expectation both times with an increase in amplitude from 0.8 to 1, but it is also conceivable that there was good response to the stimulus the first time and none whatsoever with the higher value of  $\beta$ .

- $\beta$  will be displayed graphically for the first and second half of the average of all sessions
- The two  $\beta$  values per session will be averaged and displayed graphically per sessions
- $\beta$  will be analysed after standardization in a mixed linear model with the coefficients as the dependent variable. For the within-session analysis, the first and second half of the regulation condition will be estimated (fixed effect) and session (linear fixed effect) and patient as a random effect for the intercept. For comparisons between the tasks regulation and mirror, a mixed model with condition as the fixed effect of interest, session and first/second half as a nuisance parameter and patients as a random term will be used. These analyses will be repeated for the transfer vs mirror condition.

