### **4.4.2 Within-session and between-session comparisons (CRED-nf 5b/5c)**

Mean beta band activity in  $\mu\text{V}$  for baseline, feedback and transfer trial will be displayed graphically per session.

For within-session variability, two mixed effects models (one for feedback and one for transfer) will be used. The dependent variable is the mean power in the  $\beta$  band and the fixed effects are the (constant) baseline mean power in the  $\beta$  band and the number of the trial, treated as a numerical variable (i.e. assuming linear behaviour over time). The patient is the random term.

To assess the success of the feedback relative  $\beta$  band power will be shown graphically for resting state eyes open, eyes closed, and food cue presentation at pre and post treatment. Paired t-test of the logarithms of these values will be used for formal testing with Bonferroni-Holm correction for the three states.

For comparison with a “control” condition, the difference of  $\beta$  band power on a logarithmic scale (i.e. logarithm of the ratio) from feedback to its baseline will be compared to the difference from transfer to its baseline. These differences will be treated in a mixed model with condition (feedback vs transfer) and session number fixed effects along with their interaction and patient as a random variable. The interaction term will quantify a potential learning effect, i.e. that the feedback in the later sessions is no longer necessary and the difference between the conditions gets smaller.

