## 6.11 CRED-nf checklist

1 Domain	Item #	Checklist item	Planned analysis reported in section
Pre-experiment			
	1a	Pre-register experimental protocol and planned analyses	AO
	1b	Justify sample size	SP
Control groups			
	2a	Employ control group(s) or control condition(s)	AO
	2b	When leveraging experimental designs where a double-blind is possible, use a double-blind	NA
	2c	Blind those who rate the outcomes, and when possible, the statisticians involved	SP
	2d	Examine to what extent participants and experimenters remain blinded	NA
	2e	In clinical efficacy studies, employ a standard-of-care intervention group as a benchmark for improvement	SP
Control measures			
	3a	Collect data on psychosocial factors	2.3.1., A
	3b	Report whether participants were provided with a strategy	AO
	3c	Report the strategies participants used	AO
	3d	Report methods used for online-data processing and artifact correction	6.11.3., A
	3e	Report condition and group effects for artifacts	6.11.2., A
Feedback specifications			
	4a	Report how the online-feature extraction was defined	6.11.1., A

	4b	Report and justify the reinforcement schedule	6.11.3., 6.12.1., A
	4c	Report the feedback modality and content	6.11.3., A
	4d	Collect and report all brain activity variable(s) and/or contrasts used for feedback, as displayed to experimental participants	4.3.2., 5.3.2., A
	4e	Report the hardware and software used	6.11.1., 6.11.3., 6.12.1., A
Outcome measures			
Brain	5a	Report neurofeedback regulation success based on the feedback signal	4.3.1., 4.4.1., A
	5b	Plot within-session and between-session regulation blocks of feedback variable(s), as well as pre-to-post resting baselines or contrasts	4.3.2., 4.4.2., A
	5c	Statistically compare the experimental condition/group to the control condition(s)/group(s) (not only each group to baseline measures)	4.3.2., 4.4.2., A
Behaviour	6a	Include measures of clinical or behavioural significance, defined a priori, and describe whether they were reached	4.1., A
	6b	Run correlational analyses between regulation success and behavioural outcomes	4.3.3., 4.4.3., A
Data storage			
	7a	Upload all materials, analysis scripts, code, and raw data used for analyses, as well as final values, to an open access data repository, when feasible	NA

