#### First Level Analysis

A GLM was calculated for each channel, each half (first/second half of NF), each condition (feedback/transfer/mirror) and each session of each participant, modelling event-related concentration changes with a canonical hemodynamic response via the toolbox's function *GLM* (leaving the type at the default option AR-IRLS). The general linear equation was solved with an iteratively auto-regressive whitened, weighted least-squares method (AR-IRLS) (Barker et al. 2013). This model applies an  $n^{\text{th}}$ -order AR filter derived via an Akaike model-order selection to whiten both sides of the GLM expression. All source-detector pairs within a file are solved concurrently yielding a full covariance model of the noise. The AR-IRLS method accounts for the expected presence of serially correlated errors (i.e., extracerebral components) in the optical signals due to cardiac pulsation and respiration and has been shown to have a good control of type-I error (Huppert 2016). It is not recommended to filter data if using the AR-IRLS GLM algorithm (Huppert 2016). To ensure data quality, all data were visually inspected before and after applying the AR-IRLS method.

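### In the exploratory fNIRS analysis, no planned formal test separates change specific to the regulation task from change it shares with the mirror task

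*SAP*

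**What the plan says.** SAP 4.3.2 plans two mixed models for the standardized beta weights of each patient's two selected channels.

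- **Regulation only.** "For the within-session analysis, the first and second half of the regulation condition will be estimated (fixed effect) and session (linear fixed effect"), with a random intercept for patient. Mirror data do not enter.
- **Regulation versus mirror.** "For comparisons between the tasks regulation and mirror, a mixed model with condition as the fixed effect of interest", and "session and first/second half as a nuisance parameter and patients as a random term will be used". No interaction is named.

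The section then adds: "These analyses will be repeated for the transfer vs mirror condition".

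The first-level analysis in SAP 6.11.2 produces a beta for "each half (first/second half of NF), each condition (feedback/transfer/mirror) and each session of each participant", so mirror values exist for every half and session. The checklist in SAP 6.11 cites 4.3.2 for item 5c: "Statistically compare the experimental condition/group to the control condition(s)/group(s) (not only each group to baseline measures").

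SAP 4 describes the neurophysiological analyses as exploratory and limited to completers, and SAP 4.3 calls the fNIRS plan temporary.

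**The concern.** The section is titled as covering within-session and between-session comparisons, and it has a control task to hand. Yet the only model that estimates change has no control task, and the only model with a control task forces both tasks to change by the same amount. A significant half or session effect under regulation could then come from anything that alters both tasks alike. The reverse can also happen: a shared decline can cancel a real regulation-specific gain.

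What is at stake is how the fNIRS process data are interpreted, that is, whether change under regulation can be called specific to regulation. The efficacy analysis does not depend on it.

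**Working it through.** There is no planned figure to reproduce, because 4.3.2 rests on no power or error calculation. The check is of the model terms, followed by the size of the effect under stated assumptions.

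**Terms.** Suppose the true mean beta is

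μ + c·condition + h·half + s·session + γ·(condition × half) + δ·(condition × session),

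with condition = 1 for regulation and 0 for mirror. Here h and s are change shared by both tasks; γ and δ are regulation-specific.

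- Regulation-only model: the half coefficient estimates h + γ and the session coefficient s + δ. The two parts cannot be separated.
- Regulation-versus-mirror model as planned: γ and δ are set to 0. With balanced data, h and s are absorbed by the additive terms, so the condition effect is unaffected by shared drift. It estimates the average difference only.
- With both interactions added, γ and δ are estimated directly.

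**Inputs from the documents.** 12 sessions (protocol synopsis); 2 halves (SAP 6.11.2); one arm of 26 randomized, or 21 analysed, from 42 in two pooled arms (protocol 7.4.4); α = 5% (protocol 7.4.2).

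**Assumed.** Two-sided tests, complete data, a random intercept only, and a shared shift of 0.1 to 0.3 SD. Two meanings of SD are carried: residual SD = 1, or total SD = 1 with intraclass correlation 0.3, where the residual SD is √0.7 = 0.837.

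**Half effect, regulation only.** SE = σ·√(2/(12n)). With σ = 1 this is 0.0891 (n = 21) and 0.0801 (n = 26); with σ = 0.837 it is 0.0745 and 0.0670. Under γ = 0 the rejection rate is Φ(z − 1.96) + Φ(−z − 1.96), with z = shift/SE. For a shift of 0.1 and n = 21, z = 0.1/0.0891 = 1.12, which gives 20%.

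| Shared shift | Formula, residual SD (n = 21, 26) | Formula, total SD (n = 21, 26) | Simulated, all settings |
|---|---|---|---|
| 0.1 | 20%, 24% | 27%, 32% | 20%-34% |
| 0.2 | 61%, 71% | 77%, 85% | 61%-85% |
| 0.3 | 92%, 96% | 98%, 99% | 92%-99% |

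The simulations used 3,000 to 4,000 data sets per scenario. They agree with the formula to within a point or two.

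**Session effect, regulation only.** For a shared trend of 0.1, 0.2 or 0.3 SD from first to last session, simulated rejection is 11%-15%, 30%-47% and 56%-81% across the same settings.

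**Interactions.** With no regulation-specific change, condition-by-half and condition-by-session reject in about 4% to 5.4% of simulated trials at every shared shift tried.

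**Condition main effect as planned.** It stays at about 5% under shared drift. A constant task difference of 0.3 residual SD with no change over time is significant in over 99% of runs, which shows that it answers a different question.

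**Masking.** With a true regulation-specific change of +0.3 residual SD and a shared shift of −0.3, the regulation-only half effect is significant in only 5% of runs. Condition-by-half detects the change in 66% (n = 21) to 74% (n = 26).

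**Price of the interaction.** With equal residual variance its SE is √2 ≈ 1.4 times that of the regulation-only effect: 0.0891 × 1.414 = 0.126 at n = 21 and 0.0801 × 1.414 = 0.113 at n = 26. For a true 0.3 residual SD change and no drift, simulated power is 67% to 76% for condition-by-half and 32% to 37% for condition-by-session. The regulation-only effects reach 93% to 96% and 56% to 65%, but they test total change.

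**The case against.** A good deal can be said for the plan.

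- A reader might infer that the SAP treats any half or session effect as learned regulation. It does not say so. Section 4.3.2 warns that a change in beta is hard to interpret, and the regulation-only model correctly estimates total change in that task.
- Session sits beside half in the sentence on the within-session analysis and is not named as the between-session test. The session rates above apply only if it is used that way.
- A reader might infer that item 5c is unmet. The condition main effect is a formal comparison with a control condition, and 5c does not ask for an interaction. It is met for level.
- The EEG section is not a direct precedent. In SAP 4.4.2 "The interaction term will quantify a potential learning effect, i.e. that the feedback in the later sessions is no longer necessary", but the contrast is feedback with transfer, and learning there means convergence of the two. It is not a drift control, and the EEG within-session models have no interaction either.
- Slow signal drift is partly handled before this stage by referencing intensity to baseline and by the autoregressive whitening in the first-level model (SAP 6.11.2).
- Mirror is not ignored: SAP 2.2 d lists haemoglobin values by block, task and session, so a shared shift could be seen descriptively.
- The protocol (1.2.1) addresses specific mechanisms by comparing fNIRS with EEG neurofeedback, so these beta slopes are not the trial's mechanism test.
- The rejection rates follow from the drift put in, and that size is assumed.

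All of this stands, and it limits how strongly the point can be put. It does not supply the missing test: habituation and fatigue remain possible, and a descriptive display is not a formal contrast.

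**Conclusion.** The point holds as a gap in an exploratory and provisional analysis. Section 4.3.2 can formally test whether beta under regulation changes, and whether regulation differs from mirror on average. It cannot formally test whether regulation changes differently from mirror, although the data allow it.

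The size depends on a shared shift that the documents do not quantify. A shift of 0.1 SD between halves is enough to raise the regulation-only half effect from 5% to roughly 20%-34%; at 0.3 SD it is almost always significant. These figures assume complete data from one arm of 21 to 26 patients and a random intercept only.

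The documents do not support going further, to a claim that the planned regulation-versus-mirror comparison is biased, that the checklist item is unmet, or that the sponsor will report shared change as learning. The primary endpoint analysis is untouched.

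**What to change.** In SAP 4.3.2, add condition-by-half and condition-by-session terms to the regulation/mirror model and to the transfer/mirror model, keeping the patient random term. State that any claim of regulation-specific within-session change rests on condition-by-half, and any claim of between-session change on condition-by-session. The regulation-only half and session effects can stay, reported as total change in that task.

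The cost is a few lines of SAP text and two terms per model, on betas that the first-level analysis already produces; the section is due for an update in any case. The statistical price is lower power, particularly for condition-by-session, so interaction estimates should be given with confidence intervals and a non-significant result should not be read as no change. The correction also assumes that mirror shares the drift. The documents do not describe the content or order of the mirror task, so the SAP should state why that assumption is reasonable.
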